8.1 Basic matters

8.1.1 Level of significance and confidence coefficient

When implementing tests, level of significance should be set at 2-sided 5%. Confidence interval (CI) will be 2-sided with a confidence coefficient of 95%.

8.1.2 Descriptive statistics to calculate

Unless otherwise specified, the following descriptive statistics should be calculated for each continuous variable item (excluding pharmacokinetic analysis).

Number of subjects, mean, standard deviation (SD), median, minimum, maximum, and 2-sided 95% CI of the mean

8.1.3 Number of digits displayed

(1) The number of digits to be displayed in the analysis results of demographic and other baseline characteristics (subject background), vital signs, and laboratory test should be as follows.

| Numeric content | Number of display digits |
|--|--|
| p value | 3 decimal places; however, when it is less than 0.001, it is described as “< 0.001”. |
| Proportion (percentage) | Integer part + 1 decimal place |
| Rate of change | Integer part + 1 decimal place |
| Descriptive statistics (minimum and maximum) | Same as the number of digits as original variable |
| Descriptive statistics (mean, SD, median) | Number of digits of the original variable + 1 digit |

(2) Pharmacokinetics analysis

- 1) Number of digits to be displayed for mean, SD, median, geometric mean:
 - Plasma MT-6548 concentrations ($\mu\text{g/mL}$) should be provided as 3 significant figures. Rounding to round down at 4 and up at 5.
 - The pharmacokinetics parameters should be as follows. The number of digits should be displayed as specified in “4. Calculation of Pharmacokinetics Parameters”.
- 2) Number of subjects and number of subjects with events:
 - Should be displayed as an integer.
- 3) Minimum, maximum:
 - Pharmacokinetic parameters should be displayed in the number of digits specified in “4. Calculation of pharmacokinetic parameters”. Plasma concentrations should be expressed in the same number of digits as measured ($\mu\text{g/mL}$, 3 significant digits).

4) Geometric coefficient of variation (%) (pharmacokinetic parameters other than t_{max}):

- Should be rounded and displayed to one decimal place.

Should be calculated using the following formula.

$$\text{Geometric coefficient of variation (\%)} = [\exp(\text{SD}^2) - 1]^{1/2} \times 100$$

where SD is the standard deviation after logarithmic conversion of the data.

5) Coefficient of variation (%):

- Should be rounded and displayed to one decimal place.

Should be calculated using the following formula.

$$\text{Coefficient of variation (\%)} = \text{SD}/\text{Mean} \times 100$$

SD is standard deviation and Mean is the mean.

6) Pharmacokinetic parameter (except for t_{max}) ratios and CI:

- Will be rounded and displayed to three decimal places.

7) Difference and CI of t_{max} :

- Should be rounded and displayed to two decimal places.

8) Test statistics:

- Should be rounded and displayed to two decimal places.

9) P value:

- Will be rounded and displayed to three decimal places.

When the p-value is less than 0.001, "< 0.001" is displayed.

8.2 Breakdown of subjects

8.2.1 Disposition

Analysis set: Subjects who received the study drug

Analysis methods: The breakdown by group in each analysis set should be displayed.

Items: Number of subjects treated with study drug, pharmacokinetics analysis set and its proportion, number and its proportion of subjects excluded from pharmacokinetics analysis set, number and its proportion of subjects included in safety analysis set, number and its proportion of subjects excluded from safety analysis set

8.2.2 Discontinued subjects

Analysis set: Subjects who received the study drug

Analysis method: The number and proportion of discontinued subjects should be tabulated by group. The number and proportion of subjects should be tabulated by reasons of discontinuation.

Item: Number and proportion of subjects who completed the study by group in subjects treated with the study drug, number and proportion of subjects who discontinued the study by group in subjects treated with the study drug, number and proportion of subjects who discontinued the study by reasons of discontinuation

8.3 Demographic and other baseline characteristics

Analysis set: Pharmacokinetics analysis set If pharmacokinetics analysis set and safety analysis set are different, the same analysis should be performed in the safety analysis set.

Analysis method: Key demographic and other baseline characteristics should be summarized for each group. Frequency and proportion should be provided for discrete variables and descriptive statistics for continuous variables (no calculation of 95% CI of the mean).

Table 8.3 Demographic and other baseline characteristics

| Category | Item | Type of variables |
|--------------------|--|-------------------|
| Subject background | Sex (male, female) | Dichotomous |
| | Age (years) as of informed consent | Continuous |
| | Height (cm) | Continuous |
| | Body weight (kg) | Continuous |
| | BMI (kg/m^2) | Continuous |
| | Presence of complications 2 categories: Yes, No | Dichotomous |
| | Ethnicity 2 categories: Japanese, Other | Dichotomous |

8.4 Pharmacokinetics analysis

As a general rule, pharmacokinetic analysis should be performed on the pharmacokinetics analysis set. When necessary, descriptive statistics for continuous variables should be calculated and frequency and proportion will be calculated for discrete variables.

8.4.1 Tabulation of plasma concentrations of unchanged MT-6548

Analysis set: Pharmacokinetics analysis set

Analysis method: Summary statistics (number of subjects, mean, SD, median, minimum, and maximum) for each cohort at each time point of blood collection should be calculated by treatment condition.

8.4.2 Tabulation of pharmacokinetic parameters of unchanged MT-6548

(1) Calculation of summary statistics for pharmacokinetic parameters

Analysis set: Pharmacokinetics analysis set

Analysis method: Summary statistics (number of subjects, mean, SD, coefficient of variation, median, minimum, maximum, geometric mean and, geometric coefficient of variation) should be calculated for pharmacokinetic parameters ($AUC_{0-\infty}$, C_{max} , t_{max} , AUC_{0-last} , $MRT_{0-\infty}$, Kel , and $t_{1/2}$) for each cohort by treatment condition. If the individual values of C_{max} , AUC_{0-last} , or $AUC_{0-\infty}$ become 0.000 $\mu\text{g}/\text{mL}$ or 0.0 $\mu\text{g}\cdot\text{h}/\text{mL}$, respectively, no geometric mean or geometric coefficient of variation will be calculated but “—” will be provided. No geometric mean or geometric coefficient of variation will be calculated but “—” will be provided for t_{max} .

(2) Calculation of summary statistics of ratios of pharmacokinetic parameters between treatment conditions

Analysis set: Pharmacokinetics analysis set

Subject item: Summary statistics (number of subjects, mean, SD, coefficient of variation, median, minimum, maximum, geometric mean and, geometric coefficient of variation) should be calculated for pharmacokinetic parameters ($AUC_{0-\infty}$, C_{max} , t_{max} , AUC_{0-last} , $MRT_{0-\infty}$, Kel , and $t_{1/2}$) by treatment condition. T_{max} is calculated using differences between treatment conditions.

8.4.3 Evaluation of tabulation of pharmacokinetics after administration of MT-6548 tablets alone or in combination with oral iron supplements or iron-containing phosphate binders

Analysis set: Pharmacokinetics analysis set

Analysis methods: For each cohort, pharmacokinetic parameters, $AUC_{0-\infty}$, C_{max} , and AUC_{0-last} , are logarithmically transformed, and the least squares mean (LSMean), standard errors, and the difference of LSMean (each combination therapy – monotherapy) should be calculated by analysis of variance

using a linear mixed effects model with treatment condition (monotherapy or combination therapy), treatment period, and group as fixed effects and subject as random effects.

The ratio of geometric mean (for each combination/monotherapy) and its 90% CI should be calculated by inverse logarithmic transformation of the difference of LSMean of the above obtained logarithmic values. Geometric mean ratios (for each combination/monotherapy) and their 90% CIs will be converted to % and displayed to 2 decimal places.

In addition, within-individual CV should be calculated using intra-individual variance (SD^2_{within}) of analysis of variance using a linear mixed effects model.

$$\text{Intra individual CV (\%)} = [\exp (SD^2_{within}) - 1]^{1/2} \times 100$$

[MMRM Model]

- Fixed effects: administration condition, study period, group
- Methods of freedom adjustment: Kenward-Roger method
- Random effects: subjects

8.4.4 Scatter plot chart of plasma concentration of unchanged drug

Analysis set: Pharmacokinetics analysis set

Subject item: Plasma concentrations of unchanged MT-6548 by subject

Drawing method: A time-course chart (linear and semilogarithmic plots) for plasma concentrations of unchanged drug over time following MT-6548 tablet administration should be prepared for each cohort by administration condition.

Analysis set: Pharmacokinetics analysis set

Subject item: Mean and SD of plasma concentrations of unchanged MT-6548 by administration condition

Drawing method: Time course diagram (linear plot) of the mean + SD and time course diagram (semilogarithmic plot) of the mean of plasma concentration of unchanged drug versus time after administration of MT-6548 tablets by treatment condition for each cohort.

8.4.5 Time course diagram of pharmacokinetic parameters after administration of MT-6548 tablets alone or in combination with oral iron supplements or iron-containing phosphate binders

Analysis set: Pharmacokinetics analysis set

Subject item: Individual values and mean \pm SD of pharmacokinetic parameters of unchanged MT-6548

Drawing method: Spaghetti plots should be prepared for each cohort regarding changes over time in pharmacokinetic parameters ($AUC_{0-\infty}$, C_{max} , and AUC_{0-last}) from monotherapy to each combination therapy in each subject. The mean \pm SD for each treatment condition should also be plotted.

8.5 Safety analysis

The data should be tabulated for the safety analysis population. When necessary, frequency and proportion should be calculated for discrete variables and descriptive statistics for continuous variables.

8.5.1 Summary of adverse events and adverse drug reactions

The number (number of subjects with adverse events) and proportion of subjects in whom the following adverse events are observed at least once should be calculated in each cohort.

- Adverse event
- Adverse drug reaction
- Serious adverse event
- Serious adverse drug reaction
- Adverse event leading to discontinuation
- Adverse event leading to death (adverse event of fatal outcome)

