9.2.4.1 Objective findings

Investigators/subinvestigators will promptly check the results and record day of confirmation and confirmation results (clinical significance) for all the following tests.

(1) General laboratory tests

The following laboratory tests will be performed on the day of screening (any time), in the evaluation period (immediately before administration of the study drug, and 24 hours after administration of the study drug in each period), and at discontinuation (only for subjects withdrawn from the study after the start of administration of the study drug, any time). The target volume of blood collected each time is approximately 2 mL for 1), 11 mL for 2), and 11 mL for 4) below, and the amount of urine to be collected is approximately 10 mL. The collection date and purpose of the blood sample will be recorded in the CRF. The study site will report the test results (excluding 4)) to the sponsor only for subjects who receive the study drug.

1) Hematology tests:

RBC count, haemoglobin, hematocrit, WBC count, platelet count, WBC fraction (neutrophils, eosinophils, monocytes, lymphocytes, basophils)

2) Blood biochemistry tests:

AST (GOT), ALT (GPT), ALP, LDH, γ -GTP, total protein, albumin, blood glucose, total cholesterol, LDL-C, HDL-C, triglycerides, total bilirubin, urea nitrogen (BUN), serum creatinine, uric acid, CPK, Na, K, Cl, Ca, P, Mg, C-reactive protein, serum iron, ferritin, TSAT

- 3) Urinalysis (qualitative)
Glucose, protein, urobilinogen, occult blood, specific gravity, pH, ketones, bilirubin
- 4) Immunology tests: Only at screening
HBs antigen, serological test for syphilis, HCV antibody, HIV antigen or antibody

(2) Vital signs (blood pressure, pulse rate, body temperature)
Blood pressure (systolic and diastolic blood pressure), pulse rate, and axillary body temperature (ascertained to the first decimal place) will be measured for subjects in the seated position on the day of screening (any time), Day -1 (day before administration of the study drug), in the evaluation period (immediately before administration of the study drug, 24 hours after administration of the study drug, and 48 hours after administration of the study drug in each period), and at discontinuation (only for subjects withdrawn from the study after the start of administration of the study drug; any time). Date and results will be recorded in CRFs.
Measurements will be made before blood sampling when possible, and after 5 minutes at rest.

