13.3.2 Safety

Adverse events and adverse drug reactions will be compiled for each set of administration conditions, and the frequencies of occurrence will be calculated for each. For the results of general laboratory tests and vital signs measurements, summary statistics (number of subjects, mean, standard deviation, median, minimum, and maximum) will be calculated and displayed for each measurement time under each set of administration conditions. Changes from baseline to each measurement time in 12-lead ECG data will be displayed in shift tables for each set of administration conditions.

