| Abbreviation | Full term |
|------------------|--|
| AUC | Area under the plasma concentration-time curve |
| C _{max} | Maximum plasma concentration |
| Kel | Apparent terminal elimination rate constant |
| MRT | Mean residence time |
| t _{1/2} | Terminal elimination half-life |
| T _{max} | Time to reach maximum plasma concentration |
| R ² | Adjusted R ² |
| R | Correlation coefficient |

Definitions of terms

| Term | Definitions |
|------------------------------|--|
| Study phase | Cohort 1: Period 1 is defined as the period from the time of administration of the study drug on Day 1 to before administration of the study drug on Day 4. Period 2 is defined as the period from the time of administration of the study drug on Day 4 to before administration of the study drug on Day 7. Period 3 is defined as the period from the time of administration of the study drug on Day 7 to the end of the prescribed tests on Day 10. Cohorts 2 and 3: Period 1 is defined as the period from the time of administration of the study drug on Day 1 to before administration of the study drug on Day 4. Period 2 is defined as the period from the time of administration of the study drug on Day 4 to the end of the prescribed tests on Day 7. |
| Conditions of administration | Cohort 1: Administration of MT-6548 tablets alone, coadministration of MT-6548 tablets and sodium ferrous citrate formulation, or coadministration of MT-6548 tablets and ferric citrate hydrate tablets Cohort 2: Administration of MT-6548 tablets alone or coadministration of MT-6548 tablets and sucroferric oxyhydroxide chewable tablets Cohort 3: Administration of MT-6548 tablets alone or coadministration of MT-6548 tablets and ferrous sulfate sustained-release tablets |

1. Introduction

This is a document that shows more detailed contents in addition to the study protocol on the statistical analysis plan of “A Clinical Pharmacological Study to Evaluate the Effects of Oral Irons and Iron-containing Phosphate Binders on the Pharmacokinetics of MT-6548 in Healthy Male Volunteers.”

2. Study Objectives and Design

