8.5.3 Summary of adverse events and adverse drug reactions by severity

The number of subjects and incidence rate should be calculated for adverse events and adverse drug reactions by severity for the overall and for individual events classified by SOC and PT for each treatment condition in each cohort.

The tabulation method by severity (severe, moderate, mild) is as follows.

- (1) When adverse events of different severity occur in the same subject

The most severe adverse event should be counted as 1 subject.

(2) When multiple adverse events with the same degree occur in the same subject

The same severity should be counted as 1 subject.

(3) When multiple same adverse events occur in the same subject

The most severe adverse event should be counted as 1 subject.

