8.5.4 Laboratory test values

For hematology, blood biochemistry, and urinalysis (specific gravity, pH), descriptive statistics should be calculated for each treatment condition in each cohort at each evaluation time point. The changes from baseline at each evaluation time point should be summarized in the same manner.

Concerning qualitative urinalysis (glucose, protein, urobilinogen, occult blood, ketone bodies, bilirubin), a shift table composed of frequency tabulation by category at each evaluation time point and decision results at baseline and each evaluation time point in each evaluation period should be provided for each administration condition in each cohort.

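### Does the cohort-only wording of the adverse event overview in SAP 8.5.1 hide the condition under which a serious event arose?

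*SAP*

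**What the plan says.** SAP 8.5.1 defines the adverse event overview. Its six lines are any adverse event, any adverse drug reaction, serious adverse event, serious adverse drug reaction, adverse event leading to discontinuation, and fatal adverse event. For each line it wants the number and proportion of "subjects in whom the following adverse events are observed at least once should be calculated in each cohort". Condition of administration is not mentioned.

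The neighbouring text is fuller. Protocol 13.3.2 states: "Adverse events and adverse drug reactions will be compiled for each set of administration conditions". SAP 8.5.3 tabulates severity "for the overall and for individual events classified by SOC and PT for each treatment condition in each cohort". For laboratory values, SAP 8.5.4 says that "descriptive statistics should be calculated for each treatment condition in each cohort at each evaluation time point". SAP 8.5.5 (ECG) and 8.5.6 (vital signs) follow the same pattern. SAP 8.5.2, the table by system organ class and preferred term, states no grouping, but it sorts terms by subject counts under monotherapy and then under combination therapy.

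The SAP's definitions of terms set out the conditions cohort by cohort. For Cohort 2, for example, they are: "Administration of MT-6548 tablets alone or coadministration of MT-6548 tablets and sucroferric oxyhydroxide chewable tablets".

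**The concern.** In a parallel-group trial a count by cohort might be enough. Here each subject is planned to receive MT-6548 alone and one or two coadministrations, so a cohort count pools the reference condition with the test conditions. The cohorts themselves differ in meal timing and in the iron product used, so comparing them says nothing direct about the effect of adding iron. The study objective includes safety under coadministration, and the comparison that serves it is between conditions within a cohort.

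Read literally, the overview would show that a serious or fatal event occurred in, say, Cohort 2, but not whether it followed MT-6548 alone or MT-6548 with sucroferric oxyhydroxide. SAP 8.5.3 does not supply the answer directly, because it splits by severity, and Protocol 9.2.4.2 defines severity separately from seriousness and outcome. At stake is whether a reader of the safety tables could attribute the most important events to a condition.

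**Working it through.** No sample size, power or event figure is involved, so the check sets the sections side by side and traces whether each overview line can be assigned to a condition.

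**1. What the protocol promises.** Protocol 13.3.2 commits to adverse events and adverse drug reactions, with frequencies, for each set of administration conditions. It does not promise separate serious, fatal or discontinuation lines.

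**2. What SAP 8.5.3 delivers.** It gives an overall severity table by condition within cohort, for adverse events and for adverse drug reactions. A subject with events of different severity is counted once, at the worst grade. Mild, moderate and severe therefore add up to the number of subjects with any event under that condition. Two of the six lines in 8.5.1 are covered in this way, and they are the two that Protocol 13.3.2 names.

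**3. What is left.** 6 − 2 = 4 lines have no separate count by condition in the text available: serious events, serious reactions, events leading to discontinuation, and fatal events. SAP 8.2.2 helps with discontinuation only in part: "The number and proportion of discontinued subjects should be tabulated by group", with reasons. Group is a treatment sequence, not a condition.

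**4. Whether those events can be placed.**
- Protocol 9.2.4.2 has each adverse event entered in the case report form with onset date, a category for time of onset, seriousness, causal relationship and outcome.
- Protocol 12.2 adds the withdrawal date and, where an adverse event is the reason, its name.
- Protocol 9.2.4 tabulates adverse events by evaluation period. Protocol 13.2 and SAP 7.4 settle the borderline case: a predose finding in Period 2 or 3 judged to be an adverse event belongs to the preceding period. Protocol 5.2 and the SAP definitions close the last period at the end of the prescribed tests.
- The design tables give one condition for each group and period. Cohort 1 has 3 groups × 3 periods = 9 such pairs, and Cohorts 2 and 3 have 2 × 2 = 4 each, so 9 + 4 + 4 = 17 pairs, each with exactly one condition. Once the period is known, the condition is known.
- Protocol 11.1 requires an immediate notice and a detailed written report for every serious event, so such events are described individually whatever the overview table shows.

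**5. What the wording changes.** The definitions give 3 + 2 + 2 = 7 cohort-by-condition columns, and a literal reading of 8.5.1 gives 3 cohort columns. That is a difference in layout. The geometric mean ratios and their 90% confidence intervals do not use this table, and neither document attaches a safety decision rule to it.

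**6. Whether pooling was intended.** The SAP introduction presents the document as adding detail to the protocol, so 13.3.2 still governs where the SAP is brief. Section 8.5.2 names no grouping at all, yet its sort order works only with separate monotherapy and combination counts. This points to compressed drafting rather than a decision to pool.

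**The case for a change.** The best argument for a change is that 8.5.1 departs from the protocol's stated grouping and from four sibling sections without giving a reason, in a design where cohort is the wrong unit for a safety comparison. Individual serious event reports are no substitute for a prespecified count over the subjects dosed under each condition, and the repair would be a single phrase.

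Part of this stands. The inconsistency is real, a cohort count does pool conditions, and the subjects dosed under a condition are the natural denominator. The protocol mismatch, however, is narrower than it looks, because the categories that 13.3.2 names are produced by condition through 8.5.3. The remaining counts follow from data and period rules already in place, and their denominators follow from the dosing records required by Protocol 9.2.2. Nor does 8.5.1 forbid a further split: it says what is calculated in each cohort and does not exclude condition columns.

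The SAP contents page also announces a list of output tables, where column layouts would normally be fixed. The text available stops at the references heading, so it cannot be shown that the SAP as a whole omits the split.

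**Conclusion.** The concern does not call for a change. SAP 8.5.1 is worded less fully than the sections around it. Two of its six lines are available by condition from 8.5.3, and the other four can be assigned to a condition from information the protocol already requires. A programmer working under Protocol 13.3.2 would add the condition columns, and a reader of the clinical study report could in any case trace each serious or fatal event to its period and hence to its condition. Following the plan as written leaves the pharmacokinetic results untouched and the safety conclusions sound.

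This rests on two assumptions: that onset, seriousness and outcome are recorded as Protocol 9.2.4.2 requires, and that events are assigned to periods under the existing rules. It does not depend on the unseen list of output tables. If that list has condition columns, nothing remains beyond a drafting slip. If it does not, the split can still be produced without new data or a new rule. The documents give no event rates, and none are assumed.
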